5.4.2.3 Detection rates

The detection rate (DR) will be calculated as $(\text{TP}+\text{FP})/n$ from the above table.

The point estimate (expressed in percentage) of the DR will be presented at the region level and at the subject level, as well as for the prostatic bed, other pelvic disease and distant metastases. These rates will be presented for all subjects from the FAS and PPS, overall and across a range of baseline PSA values:

- 0 – 0.2
- >0.2 – 0.5
- >0.5 – 1.0
- >1.0 – 2.0
- 2.0 – 5.0
- 5.0 – 10.0
- >10.0

to determine the optimum PSA threshold for lesion detection.

The detection rates will also be summarised across the following baseline Gleason score categories: ≤ 6 , 7, 8 and ≥ 9 .

All detection rate data will be listed.

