The number, percentage and exact 95% confidence interval (CI) of subjects with and without a change in management plan after ¹⁸F-fluciclovine PET/CT scan results become available will be presented for the EAS. In addition, the number and percentage of subjects with changes categorised as major or other will be presented along with its 95% CI. These summaries will be repeated separately for subjects with a positive and a negative ¹⁸F-fluciclovine PET/CT scan and for subjects without prostatectomy and with prostatectomy. All these summaries will be repeated using the PPS.

Details of the intended management plan, revised management plan and categorisation of change in management plan will be listed.

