5.4.2 Secondary Efficacy Analyses

5.4.2.1 Change in actual management plan

The number, percentage and exact 95% CI for the percentage of subjects in the EAS with clinically significant deviations in actual management from the revised management plan after ¹⁸F-fluciclovine PET/CT scan results become available will be presented for overall and for subjects with positive and with negative ¹⁸F-fluciclovine PET/CT scans.

All management plan deviations will be listed in full.

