5.4.2.2 Diagnostic performance of ¹⁸F-fluciclovine

Diagnostic performance will be assessed by calculating sensitivity, specificity, Positive Predictive Value (PPV), and Negative Predictive Value (NPV), using subject based analyses. Further calculations will be made for intra-prostatic / prostate bed and extra-prostatic disease. Reference tests will be the adjudication panel decision. The Adjudication Panel will follow the Adjudication Manual that prospectively documents the processes to be used to determine a decision concerning the result of the ¹⁸F-fluciclovine PET/CT scan vs standard of truth. The number and percentage of indeterminate responses will be reported.

The sensitivity, specificity, PPV and NPV will be calculated as:

- Sensitivity = $TP / (TP + FN)$
- Specificity = $TN / (FP + TN)$
- PPV = $TP / (TP + FP)$
- NPV = $TN / (FN + TN)$

where TP, TN, FP and FN refer to true positive, true negative, false positive and false negative results respectively.

Definitions of these summaries will be based on the table below.

		Reference tests		
		Positive	Negative	
Fluciclovine (¹⁸ F) scan results	Positive	True Positive (TP)	False Positive (FP)	TP+FP
	Negative	False Negative (FN)	True Negative (TN)	FN+TN
		TP+FN	FP+TN	n

The number, percentage and exact 95% CIs of TP, FP, FN and TN, as well as the point estimates (expressed in percentages) and their associated exact 95% CIs, of the Sensitivity, Specificity, PPV and NPV, will be presented at the subject level and the region level for the FAS, where the region level estimates will be calculated separately for each region: prostatic region and extra-prostatic region. The region level results will be derived at the subject level for each region resulting in one outcome for each subject in each region. For the subject level analysis, if a subject has at least one positive result, the subject will be categorised as positive. If all of a subject's results are negative the subject will be categorised as negative. For the region level analysis, if a subject has at least one positive result from the prostatic region the subject will be categorised as positive for the prostatic region. If all results related to the prostatic region are negative for a subject, that subject will be categorised as negative for the prostatic region. Similar classification rules apply for the extra-prostatic region.

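### SAP 5.4.2.3 states no exact 95% CI for the detection rate, which protocol 14.2 requires, and takes the rate from the adjudicated 2x2 table although only the scan result is needed

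*SAP*

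**What the plan says.** SAP 5.4.2.3 states: "The detection rate (DR) will be calculated as" (TP+FP)/n from the table above it. That table, in SAP 5.4.2.2, crosses the scan result (positive or negative) with the reference test (positive or negative), and the reference test is the adjudication panel decision. The table has four cells and no place for an undetermined result, although the same section expects some: "The number and percentage of indeterminate responses will be reported".

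On presentation, SAP 5.4.2.3 says "The point estimate (expressed in percentage) of the DR will be presented at the region level and at the subject level", then adds prostatic bed, other pelvic disease and distant metastases. On population it says "These rates will be presented for all subjects from the FAS and PPS". It mentions no confidence interval.

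Protocol 14.2 describes the detection rate as the proportion of positive PET/CT results and specifies an exact binomial 95% interval for it. The matching objective (protocol 3.2, SAP 3.1) is the fraction of patients with evidence of recurrence as judged from imaging. Protocol section 14 says that the SAP will contain any modification of the planned analysis. SAP 3.5 lists one, the reference standard for PPV.

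**The concern.** The detection rate is the second and third secondary endpoint. There are two separate faults.

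- **Interval.** The protocol specifies one and the SAP section that governs the output does not mention it. If the tables follow the SAP text, a protocol-specified result is lost without a declared change.
- **Formula.** An imaging-only rate needs no reference standard. Taking it from a table that requires a panel decision could make it depend on which scans received a determinate decision. Two sentences later the section asks for all FAS and PPS subjects. If any decision is missing or indeterminate, both instructions cannot be met.

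**Working it through.** **1. Source of the planning figures.** The documents give no precision target for the detection rate, so the inputs come from the sample-size section (protocol 14.4), whose chain reproduces:

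- Clopper-Pearson at 30%, n = 89: 0.207 to 0.406, width 0.199, as printed.
- 89/0.40 = 222.5, so 223.
- With 248 subjects, P(at least 89 positive at 40%) = 0.918, above the stated 90%.
- 248/0.85 = 291.8, so 292. The stated ceiling is 330.

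**2. The interval that is not stated.** With x positive scans of n, the lower limit is the 0.025 quantile of Beta(x, n-x+1) and the upper limit is the 0.975 quantile of Beta(x+1, n-x). At 40% positivity:

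| Scanned n | Positive x | Rate | Exact 95% CI | Width (points) |
|---|---|---|---|---|
| 248 | 99 | 39.9% | 33.8 to 46.3 | 12.5 |
| 292 | 117 | 40.1% | 34.4 to 45.9 | 11.5 |
| 330 | 132 | 40.0% | 34.7 to 45.5 | 10.8 |

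292 and 330 are enrolment figures. Using them as n assumes that nobody is lost before the scan. 248 is the figure before the 15% allowance for data loss.

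**3. The SAP's other proportions.** SAP 5.4.1: "The number, percentage and exact 95% confidence interval (CI) of subjects with and without a change in management plan". SAP 5.4.2.1: "The number, percentage and exact 95% CI for the percentage of subjects in the EAS". SAP 5.4.2.2: "as well as the point estimates (expressed in percentages) and their associated exact 95% CIs, of the Sensitivity, Specificity, PPV and NPV". SAP 5.4.2.4 also states exact intervals, for PSA response. SAP 5.4.2.2 gives intervals for the TP, FP, FN and TN counts as well, but intervals for TP and FP separately do not give one for their sum. The detection rate is the exception.

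**4. When the formula departs from the endpoint.** TP+FP is the total of the scan-positive row. If every scanned subject has a determinate decision, TP+FP equals the number of positive scans, n equals the number scanned, and the two definitions agree. They also agree if decisions are equally complete in both rows. With 90% complete in each row of the 248 example, the rate is 89/223 = 39.9%, unchanged.

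They differ only if completeness depends on the scan result, or if the numerator comes from the table and the denominator from the FAS. The documents do not give completeness, so the following is illustration only. Take 330 scanned, 132 positive, and u scans without a determinate decision (u is **assumed**):

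- All u are positive scans: (132-u)/(330-u).
- All u are negative scans: 132/(330-u).
- Table numerator over the FAS, all u positive: (132-u)/330.

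| Assumed u | All positive, table n | All negative, table n | All positive, FAS n |
|---|---|---|---|
| 16 (about 5%) | 116/314 = 36.9% | 132/314 = 42.0% | 116/330 = 35.2% |
| 33 (10%) | 99/297 = 33.3% | 132/297 = 44.4% | 99/330 = 30.0% |

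The scan-only rate is 40.0% throughout. These are extremes, since they put every undetermined scan in one row.

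**The case against.** The best defence is that the formula is not wrong, only loosely worded. The panel decision cancels in the scan-positive row total. The FAS is defined by having had the scan (SAP 4.1), SAP section 2 makes the analysis set the default denominator, and SAP 5.4.2.3 names the FAS and PPS. Together these give positive scans over the FAS, which is the protocol's definition. Most of this stands, and it is why the formula half is put conditionally. What remains is that the section points to the table for its n and does not say which n governs when the two differ.

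A reader might infer that many scans will lack a decision because biopsy is optional, so that the detection rate is biased. The documents do not support that. Protocol 14.2 has the panel compare results for each patient, using histology, other imaging and response to treatment, so no biopsy does not mean no decision. Its qualifier about what can be calculated concerns the accuracy measures, not the detection rate. The synopsis describes a narrower panel task, limited to lesions with biopsy or MRI, but SAP 3.5 moves away from that basis for PPV. The Adjudication Manual was not available. Undetermined results are anticipated, but their number is not stated.

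A reader might also infer that the sponsor decided to drop the interval. The SAP does not say so. The interval follows directly from count and n, and the separate output shells, which were not available, may contain it. The SAP should still match the protocol or declare the change.

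**Conclusion.** Both textual faults are real, and they differ in weight. The absent interval follows from the text alone, with high confidence. At 40% positivity, an uncertainty of about 11 to 12.5 points in total width would go unreported. That size rests on the planning positivity and on 248 to 330 subjects being scanned.

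The formula half holds with moderate confidence, as an ambiguity that can do harm if followed literally. Any bias is zero if adjudication is complete, or equally complete for positive and negative scans with the table's n as denominator. The documents fix neither its size nor its direction, so the shifts in the illustration are not estimates.

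The endpoint is descriptive, and scan results and adjudication decisions are listed, so an error could be corrected later. The primary analysis and the sample size are not affected. This is a minor correction to a secondary endpoint.

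**What to change.** Change two sentences in SAP 5.4.2.3.

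1. Replace the formula sentence only, for example with: *DR = number of FAS (PPS) subjects with a positive site-read scan / all FAS (PPS) subjects, irrespective of the adjudication decision.*
2. In the next sentence, ask for the point estimate **and the exact (Clopper-Pearson) 95% CI**. Keep its list of levels as it stands: region, subject, prostatic bed, other pelvic disease and distant metastases. Shortening the list to regions could lose the third secondary endpoint, because the two main regions in SAP 5.3 pool pelvic nodes with distant sites.

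If the interval was left out on purpose, declare it in SAP 3.5.

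Two additions are optional and not required by the protocol. One is a rule for equivocal site reads: the SAP says "if a subject has at least one positive result, the subject will be categorised as positive" and covers the all-negative case, but nothing between. The other is exact intervals by PSA band and Gleason category, which would help because the bands are used to look for a PSA threshold.

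The cost is two SAP sentences and minor programming. No new data are needed, because the site report is already recorded in the eCRF (protocol 11.5).

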1.1 Overview of Clinical Studies

Published data from single-institution studies of ^{18}F -fluciclovine PET have preliminarily demonstrated its operating characteristics in over one hundred study subjects with recurrent prostate cancer after curative-attempt primary therapy (see Figure) (5,6,7). Dosimetry has previously been described and is notable for a favorable pelvic imaging profile because of low levels of uptake within the urinary bladder. ^{18}F -fluciclovine PET/CT has demonstrated approximately 90% sensitivity and 40-67% specificity for detection of cancer in the prostate bed. It has demonstrated 55-100% sensitivity and more than 95% specificity for the detection of disease outside of the prostate bed. Multi-center study is needed to determine the clinical impact of localization of suspected prostate cancer recurrence by ^{18}F -fluciclovine PET/CT, specifically the impact on patient management.

The goal of the proposed study is to further evaluate the impact of ¹⁸F-fluciclovine PET/CT of prostate cancer in a multi-institution study. We hypothesize that by identifying disease in or outside of the prostate bed—either in regional lymph nodes or distant disease sites, ¹⁸F-fluciclovine PET/CT will impact the approach to patient management. This typically involves prostate bed irradiation in patients with prior prostatectomy, and a combination of additional focal therapy such as radiotherapy, cryotherapy, and/or systemic therapy in patients treated initially with local radiotherapy or brachytherapy. We propose a study of men who have undergone definitive treatment of localized prostate cancer (e.g. by prostatectomy, local radiotherapy, brachytherapy) and are presenting with rising PSA levels indicative of recurrent or persistent disease. We have chosen to study patients without evidence of disease (or with equivocal findings) by standard imaging (bone scintigraphy and CT or MRI) and with PSA levels in the range where imaging findings outside the prostatic bed would be expected to have a significant impact on treatment. Study participants with negative or equivocal conventional staging studies (^{99m}Tc-MDP bone scintigraphy /NaF PET-CT (dependent on standard of care at the institution) and abdominal-pelvic CT or MRI) will undergo ¹⁸F-fluciclovine PET/CT.

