3.2 Secondary Objectives

1. To measure the fraction of patients for whom ^{18}F -fluciclovine PET/CT leads to a change of actual management by comparison with the intended management plan before ^{18}F -fluciclovine PET/CT.
2. To estimate the fraction of patients in whom ^{18}F -fluciclovine PET/CT yields evidence of recurrent disease on the basis of imaging results.
3. To estimate 1) the rates of detecting regionally recurrent disease (i.e., prostatic bed-only and/or pelvic disease outside of the bed) and 2) the rate of detecting distant metastases (i.e., bone metastases, visceral metastases, or non-regional nodal metastases) with ^{18}F -fluciclovine PET/CT in the study population.
4. To determine 1) the PPV of ^{18}F -fluciclovine PET/CT to detect regionally recurrent disease and 2) the PPV of ^{18}F -fluciclovine PET/CT to detect distant metastases in the study population in patients who undergo optional biopsy of ^{18}F -fluciclovine PET/CT findings or have documentation of disease status based on other imaging and/or follow-up data. For soft tissue disease these calculations will be limited to those patients who undergo a confirmatory biopsy and for bone disease those with confirmatory findings on MRI any time during the 6-month follow up. The denominator for the analysis will be [lesions biopsied + bone lesions].
5. To explore differences in estimated cost of treatment plans determined prior to and following ^{18}F -fluciclovine PET/CT.

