14.2 Analysis of Secondary Endpoints

For the evaluation of the secondary endpoint examining actual impact on therapy, questionnaires obtained pre-FACBC will be compared to treatment executed post-¹⁸F-fluciclovine PET/CT to calculate the fraction of cases with a change in management (versus no change in planned management). For the estimation of detection rate, the proportion of the ¹⁸F-fluciclovine -PET/CT positive results, 95% confidence interval will be calculated using the Exact method for a binomial distribution.

For each patient a comparison will be made of the results of the ¹⁸F-fluciclovine PET/CT results, any histopathology results, results of any other imaging and also for the clinical response to treatment(s) (standard of truth) by an Adjudication Panel. The PPV, NPV, sensitivity and specificity will be calculated, where possible, at lesion or regional or patient level. The PPV will be calculated separately for patients undergoing optional biopsy for (1) regional disease and (2) distant disease. The 95% confidence interval will be calculated using the Exact method for a binomial distribution. The Adjudication Panel will follow the Adjudication Manual that will prospectively document the processes to be used to determine a decision concerning the result of the ¹⁸F-fluciclovine PET/CT scan vs standard of truth.

Rates of disease detection (radiographic only and confirmed by pathology or MRI) will be described

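### SAP 5.4.2.3 draws an optimum PSA threshold from scan-positive rates by PSA band, but sets no criterion, and a rate that simply rises with disease prevalence has no optimum

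*SAP*

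**What the plan says.** SAP 5.4.2.3 states: "The detection rate (DR) will be calculated as" (TP+FP)/n, taken from the two-by-two table in SAP 5.4.2.2. On reporting it says: "The point estimate (expressed in percentage) of the DR will be presented at the region level and at the subject level", and also for the prostatic bed, other pelvic disease and distant metastases. The rates are shown for the FAS and PPS across seven baseline PSA bands, and the stated purpose of the banding is "to determine the optimum PSA threshold for lesion detection". The section names no target level, loss function, model or confidence interval.

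Three other places bear on this:

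- Protocol 3.2 sets the detection objective as the fraction of patients in whom the scan "yields evidence of recurrent disease on the basis of imaging results".
- Protocol 14.2 plans an interval for the detection rate ("95% confidence interval will be calculated using the Exact method for a binomial distribution") and adds: "Rates of disease detection (radiographic only and confirmed by pathology or MRI) will be described".
- SAP 5.4.2.2 presents "The number, percentage and exact 95% CIs of TP, FP, FN and TN", together with PPV, and repeats these summaries in the same PSA bands. Its subgroup analyses are conditional on there being enough data.

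**The concern.** An optimum requires something to be traded off, or at least a level to be reached, and SAP 5.4.2.3 provides neither. The reader of the table is left to choose. If the rate climbs with PSA, the highest band wins by construction. If it does not climb smoothly, the cut is picked after the results are known, from point estimates with no intervals.

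There is a secondary problem. Every positive scan counts as a detection, whether or not the adjudication panel agrees, so part of the rate in each band may be false positives. At stake is a statement about PSA and lesion detection that would be reported as a finding of the trial although the planned analysis cannot support it.

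**Working it through.** **The plan's own figures.** The documents give no detection rate, disease prevalence or sample size for any PSA band. The nearest derived figure is enrolment (protocol 14.4), and it reproduces: 89/0.40 = 222.5, so 223; 25 added gives 248; 248/0.85 = 291.8, so 292. It is not in dispute and is used only in step 5.

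**Inputs.** Protocol 1.1 gives "approximately 90% sensitivity and 40-67% specificity for detection of cancer in the prostate bed". Outside the bed it gives sensitivity of 55-100% and specificity above 95% (0.95 is used here as the worst case). Disease prevalence in a band, π, is an assumption and is varied. Sensitivity (Se) and specificity (Sp) are assumed constant across bands.

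**1. Is there an optimum?**

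- Adjudicated detection: TP/n = Se × π.
- SAP rate: DR = Se × π + (1 − Sp)(1 − π) = (1 − Sp) + (Se + Sp − 1) × π.
- In the bed, DR = 0.33 + 0.57π at Sp 0.67, and 0.60 + 0.30π at Sp 0.40.

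Both measures are straight lines rising with π, and neither has an interior maximum. Replacing DR by TP/n would therefore not create an optimum. What is missing is the criterion.

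**2. Direction for a fixed target.** On a common denominator, DR − TP/n = FP/n, which is never negative. If both rates rise with PSA, DR reaches any given level at the same PSA as TP/n or a lower one. This needs no prevalence figure, but it does need a target, and the SAP sets none. For a 50% target in the bed, TP/n gets there at π = 0.50/0.90 = 0.56. DR gets there at π = (0.50 − 0.33)/0.57 = 0.30 with Sp 0.67. With Sp 0.40 it is already at 0.60 when π = 0.

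**3. Size, by assumed prevalence.**

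| π | Bed TP/n | Bed DR, Sp 0.67 | Bed DR, Sp 0.40 | Outside bed TP/n | Outside bed DR, Sp 0.95 |
|---|---|---|---|---|---|
| 0.1 | 0.09 | 0.39 | 0.63 | 0.055-0.10 | 0.10-0.145 |
| 0.2 | 0.18 | 0.44 | 0.66 | 0.11-0.20 | 0.15-0.24 |
| 0.5 | 0.45 | 0.62 | 0.75 | 0.275-0.50 | 0.30-0.525 |
| 0.8 | 0.72 | 0.79 | 0.84 | 0.44-0.80 | 0.45-0.81 |

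In the bed, moving from π = 0.2 to 0.8 raises TP/n by 54 points and DR by only 34 (Sp 0.67) or 18 (Sp 0.40). Outside the bed the excess is 0.05 × (1 − π), so never more than 5 points, and the same contrast is 33-60 points for TP/n against 30-57 for DR.

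**4. Consistency with the planning assumption.** Protocol 14.4 assumes about 40% of scans are positive. Any-site positivity in a subject cannot be lower than bed positivity. Sp 0.40 puts bed positivity at 60% or more, which is incompatible. At Sp 0.67, a rate of 0.40 implies π = (0.40 − 0.33)/0.57 = 0.12. The bed columns show a mechanism and are not a forecast.

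**5. Precision.** Splitting 292 equally over seven bands gives about 41 per band. With 16/41 positive, the exact 95% CI is 0.24-0.56, a width of 0.31. The equal split is illustrative. The lowest band (0-0.2) should be almost empty, given the PSA entry criteria in protocol 6.2.

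**The case against.** The strongest reply is that the table itself is sound and the rest is one loose clause. Four parts of that reply stand.

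- Counting all positive scans is what the protocol's imaging-based objective calls for, so the formula is not an error.
- SAP 5.4.2.2 already plans TP, FP and PPV in the same PSA bands, so any inflation would be visible to a careful reader.
- Outside the bed, where specificity exceeds 95%, false positives hardly matter, and SAP 5.4.2.3 reports the regions separately.
- No objective or endpoint in protocol 3.2 and 5.2 or SAP 3.1 asks for a PSA threshold, and no trial decision depends on one.

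The reply does not rescue the clause. The purpose is attached to the detection rate alone, nothing directs the reader to the TP and PPV tables when choosing a threshold, and those tables may be dropped if data are sparse. Subject-level rates are also planned, and one positive result makes a subject positive, so bed false positives can carry into them.

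A reader might go further and infer that low-PSA bands will look far better than they are, or that the threshold will be set too low for deciding whom to scan. The documents do not support this. They give no prevalence by PSA band, and the large excess is confined to the bed and to low assumed prevalence. A downward shift follows only once a target level is fixed; with no rule, the top band could equally be chosen. The clause speaks of lesion detection and does not set a rule for scanning.

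**Conclusion.** The concern holds in a limited form. As written, SAP 5.4.2.3 states an inference that its analysis cannot deliver, because the optimum is undefined and the measure has none if it rises with prevalence and prevalence rises with PSA. False positives are a secondary distortion: potentially large in the prostate bed (a floor of 33-60% at zero disease on the protocol's figures) and at most about 5 points elsewhere. The bed figures assume constant sensitivity and specificity across bands and cannot be applied directly alongside 40% overall positivity. That false positives are what prevents an optimum does not follow either, since TP/n has none. Severity is minor: the primary endpoint and every stated objective are unaffected.

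**What to change.** In SAP 5.4.2.3, replace the threshold purpose with: *to describe detection by baseline PSA*. For each band, show the detection rate with the exact 95% CI planned in protocol 14.2, beside the TP/n and PPV already planned for the same bands in SAP 5.4.2.2. Use one stated denominator for both rates.

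If a threshold is still wanted, pre-specify the target detection level and the method, report the PSA at that level with a 95% CI, and label it exploratory. State that adjudicated detection rests on subjects for whom the panel reached a determinate result. State also that verification may vary with PSA, since biopsy is optional and follows positive findings (protocol 9.2), so a threshold based on true positives could mix verification with detection.

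The cost is SAP wording and rearranged output from data already collected. The sponsor gives up the claim to an optimum.

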6.2 Inclusion Criteria

1. History of histologically confirmed adenocarcinoma of the prostate post curative-intent local treatment (radical prostatectomy, local radiotherapy, brachytherapy)
2. Suspicion of recurrent prostate carcinoma after presumed definitive therapy for primary disease, defined as
 - a. Post-prostatectomy (with/without adjuvant RT): Detectable or rising PSA level that is ≥ 0.2 ng/mL with a second confirmatory level of ≥ 0.2 ng/mL
 - b. Post radiotherapy (without RP): PSA rise ≥ 2 ng/mL over nadir
3. Negative or equivocal findings on standard-of-care imaging for restaging of disease in the previous 60 days consisting of:
 - a. Whole-body $^{99\text{m}}\text{Tc}$ -MDP bone scintigraphy or NaF PET-CT (dependent on standard of care at the institution) and
 - b. Either CT or MRI of the pelvis (or the abdomen and pelvis).
4. Being considered for salvage therapy
5. Previous cryotherapy, external beam radiation, or HiFU must have occurred at least one year in the past.
6. Previous brachytherapy treatment will have occurred at least 2 years in the past

7. Ability to understand and the willingness to sign a written informed consent

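### Detection rate by PSA band pools men with and without prostatectomy, so any PSA threshold that involves the bands from 2.0 ng/mL up is confounded with prior treatment

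*SAP*

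**What the plan says.** Protocol 6.2, criterion 2, sets two entry rules. After prostatectomy: "Detectable or rising PSA level that is ≥ 0.2 ng/mL with a second confirmatory level of ≥ 0.2 ng/mL". After radiotherapy alone: "Post radiotherapy (without RP): PSA rise ≥ 2 ng/mL over nadir".

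SAP 5.4.2.3 does not separate these groups. It states: "These rates will be presented for all subjects from the FAS and PPS, overall and across a range of baseline PSA values". The stated purpose of the bands is "to determine the optimum PSA threshold for lesion detection". The only other stratifier is Gleason score: "The detection rates will also be summarised across the following baseline Gleason score categories". No model, no adjustment for prior treatment and no criterion for an optimum are given. On precision, the section mentions only a point estimate: "The point estimate (expressed in percentage) of the DR will be presented at the region level and at the subject level". Protocol 14.2, by contrast, calls for an exact 95% confidence interval on the detection rate.

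Elsewhere the SAP does recognise prior treatment. Section 4.4.4 tabulates cancer therapies by prostatectomy status, and section 5.4.1 repeats the change-in-management summaries "for subjects without prostatectomy and with prostatectomy". The PSA-band tables of diagnostic performance in section 5.4.2.2 have no such split, and section 5.4.5 plans no subgroup analyses.

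**The concern.** The entry rules make the study population change at one of the band boundaries. A man irradiated without prostatectomy can hardly appear below 2.0 ng/mL; above it he can. If detection differs between the two groups for reasons other than PSA, the pooled rate will move at 2.0 even when PSA has no effect in either group.

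Such a difference is plausible from the documents. The lesion sites in SAP 5.3 include the peripheral zone and central gland, which apply to men who still have a prostate. The detection rate counts false positives as well as true positives, and Protocol 1.1 cites specificity of only 40-67% in the prostate bed.

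What is at stake is how the threshold would be read. With no criterion for an optimum, a reader will take it from the pooled gradient. A step at 2.0 could then be taken as a PSA effect in men of either kind when it is partly or wholly a change of case mix.

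**Working it through.** **Plan's own figure.** The documents give no number for detection rate by PSA band or by prior treatment, so there is none to reproduce. The sample-size chain in Protocol 14.4 does reproduce (89 positives; 89/0.40 = 222.5, so 223; 248/0.85 = 291.8, so 292), and none of it depends on this analysis.

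**Step 1: who can be in which band.** PSA nadir cannot be negative, so a rise of at least 2 ng/mL over nadir implies a PSA of at least 2.0 at qualification.

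| SAP band (ng/mL) | Post-prostatectomy | Post-radiotherapy, no prostatectomy |
|---|---|---|
| 0-0.2, >0.2-0.5, >0.5-1.0, >1.0-2.0 | yes | essentially none (a value of exactly 2.0 is possible) |
| 2.0-5.0, 5.0-10.0, >10.0 | yes | yes |

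**Step 2: pooled rate in a band.** Let P be the detection rate in post-prostatectomy men, N the rate in non-prostatectomy men, and q the non-prostatectomy share of the band. Then

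pooled rate = (1 - q) × P + q × N.

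Below 2.0, q is about 0 and the pooled rate is P. If neither P nor N depends on PSA, the step on crossing 2.0 is

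step = q × (N - P).

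**Step 3: numbers (all assumed).** P is set at 40%, which is the overall positivity assumed in Protocol 14.4 and not a figure the plan gives for this group. N and q are varied. Detection is flat in PSA within each group.

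| N | q = 25% | q = 50% | q = 75% |
|---|---|---|---|
| 40% | 40% (step 0) | 40% (step 0) | 40% (step 0) |
| 60% | 45% (step 5) | 50% (step 10) | 55% (step 15) |
| 80% | 50% (step 10) | 60% (step 20) | 70% (step 30) |

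For example, 0.25 × 40% + 0.75 × 80% = 70%, against 40% below 2.0. The step runs from 0 to 30 points across this grid. That is not a bound: a wider gap between N and P gives a larger step, and N below P gives a downward step that would mask a real rise. Within the upper bands, a change in q from one band to the next produces the same kind of artefact.

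**Step 4: what stratified tables would show.** In every cell of the grid, the tables with and without prostatectomy would be flat at P and N, with no step at 2.0.

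**The case against.** Several points on the other side are sound.

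- **The lower bands are not affected in this way.** If the four bands up to 2.0 hold essentially one population, a gradient among them cannot come from prior-treatment mix, and a threshold drawn there is a post-prostatectomy threshold. A reader might infer that every rise across the bands, and any threshold at all, is an artefact. The documents do not support that; the problem is confined to contrasts involving the bands from 2.0 up.
- **The separation at 2.0 is not absolute.** The full analysis set (SAP 4.1) requires only enrolment and a scan, not criterion 2. The bands use the last PSA before injection (SAP 4.4.3), which need not be the qualifying value. Footnote 1 of Protocol Appendix 1 describes the non-prostatectomy requirement as a multiple of nadir, which does not match the absolute rise in Protocol 6.2. Criterion 2 sets no PSA level for men treated only by another local method, a category that SAP 4.4.4 allows for.
- **The size is wholly assumed.** With equal detection rates it is zero.
- **The analysis is descriptive.** No objective or efficacy variable names a PSA threshold, and no test or decision depends on one.
- **Detection is also reported by region.** This helps only in part. Retained prostate tissue would act mainly on the prostatic region and the subject-level total, not directly on nodal or distant sites. But SAP 5.3 makes the prostate and the prostate bed a single region, so the regional tables do not separate men with a prostate from men without one.

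These points narrow the concern and lower its weight. They do not remove it: the SAP states a purpose that its pooled tables cannot serve across the 2.0 boundary.

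**Conclusion.** The point holds in limited form. By design, the case mix can change at 2.0 ng/mL, and the pooled tables cannot tell a PSA effect from a prior-treatment effect in any contrast involving the bands from 2.0 up. Contrasts among the lower bands are essentially within post-prostatectomy men, but a threshold found there does not carry over to irradiated men.

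The 0 to 30 point range rests on assumed detection rates, assumed group shares and no PSA effect within either group. It shows what could happen, not what will. A reader might go further and conclude that the planned threshold will be spurious, or that the main result is compromised. The first needs group-specific detection rates that the documents do not give. The second is wrong: the change-in-management analysis already has a prostatectomy split, and neither it nor the sample size uses these bands. This is a worthwhile and cheap improvement to a secondary analysis.

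**What to change.** 1. In SAP 5.4.2.3, present detection rate by PSA band separately for subjects with and without prostatectomy, using the groups already in SAP 4.4.4 and 5.4.1. Do the same for the PSA tables of SAP 5.4.2.2 where data suffice.
2. Give exact 95% confidence intervals for these rates, as Protocol 14.2 specifies.
3. Draw any PSA threshold only within these strata, or remove the optimum-threshold wording.
4. Make the bands non-overlapping: >2.0-5.0 and >5.0-10.0. As written, values of exactly 2.0 and 5.0 each fall in two bands, and the first overlap sits where the case mix changes.
5. Reconcile footnote 1 of Protocol Appendix 1 with criterion 2 of Protocol 6.2.

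The cost is extra tables from data already collected, with smaller cells. As a guide, 330 subjects spread evenly over seven bands (an assumption) give 330/7, or about 47 per band, with an exact interval of about 26% to 55% around a 40% rate. An even split of such a band leaves about 24 per stratum and a wider interval. The loss falls almost entirely on the three bands from 2.0 up, because the lower four are close to one stratum already.
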